7.1.2 Selection Criteria

7.1.2.1 Inclusion Criteria

- Patients with MDS commencing their treatment with lenalidomide after the granting of Regulatory approval for use in the treatment of MDS in the EU (EC Decision, 13-Jun-2013) and a subsequent positive reimbursement decision in the countries concerned, irrespective if the initial MDS diagnosis occurred before (prevalent patients) or after (incident patients) such date with the exception of eligible patients from the company-sponsored Connect[®] Myeloid Disease Registry (US Cohort Registry) who will be included regardless of start date of treatment
- Laboratory confirmation (morphological and cytogenetic) of MDS
- Patients with confirmed date of MDS diagnosis and lenalidomide treatment initiation
- Obtaining appropriate permission from the selected data sources to utilise the data

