7 RESEARCH METHODS

7.1 Study Design and Selection Criteria

7.1.1 Study Design

This is a post-authorisation, non-interventional, retrospective, drug-utilisation study. This study will be run in countries in the EU in which Revlimid (lenalidomide) will have been marketed in the new indication and where MDS patients will have access to the drug post EU-approval for the MDS indication. The only exception is that eligible patients from the company-sponsored Connect[®] Myeloid Disease Registry (US Cohort Registry) will be included regardless of start date of treatment to assess the secondary safety objectives (but not the primary drug-utilisation objective due to a different MDS indication approved in the US [see Section 7.4 for the US MDS approved indication]). Results from the selected data sources that represent at least 10 EU

countries, which have lenalidomide reimbursement, will be included. More EU countries will potentially be included, once they gain reimbursement.

This retrospective drug-utilisation study will include patients with MDS treated with lenalidomide, irrespective if within or outside the approved indication in the EU (eg, patients commencing lenalidomide treatment for transfusion-dependent IPSS low- or int-1-risk MDS with isolated del(5q) or with additional cytogenetic abnormalities, or IPSS risk categories int-2 or high, or patients with MDS without del(5q) will also be recorded). Both prevalent and incident MDS cases, defined as follows, are eligible for the inclusion into the retrospective drug-utilisation study:

Prevalent patients: patients whose initial MDS diagnosis is **prior** to the date of EU-approval for the MDS indication, but whose initiation of lenalidomide treatment occurs on or after the date of EU-approval for the MDS indication.

Incident patients: patients whose initial MDS diagnosis and initiation of treatment with lenalidomide is **after** the date of EU-approval for the MDS indication.

The sources of data for this study are described in Section 7.4.

The study is planned to collect retrospective data from subjects with MDS treated with lenalidomide according to the inclusion criteria, until at least 460 patients are included.

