7.1.2.2 Exclusion Criteria

- Patients receiving lenalidomide prior to regulatory approval for use in the treatment of MDS in the EU (EC Decision, 13-Jun-2013) in the countries concerned
- Patients treated with lenalidomide in an interventional therapeutic clinical trial for MDS

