7.2 Setting

7.2.1 Study Population and Cohorts

Overall population: Those MDS patients who have received at least one dose of lenalidomide and who started their treatment after lenalidomide has obtained EU Regulatory approval for the MDS indication and in countries that granted a subsequent positive reimbursement decision with the exception of eligible patients from the company-sponsored Connect® Myeloid Disease Registry (US Cohort Registry) who will be included regardless of start date of treatment.

This population will include both prevalent (patients whose initial MDS diagnosis is **prior** to the date of EU-approval for the MDS indication, but whose initiation of lenalidomide treatment occurs on or after the date of EU-approval for the MDS indication) and incident patients (patients whose initial MDS diagnosis and initiation of treatment with lenalidomide is **after** the date of EU-approval for the MDS indication).

MDS licensed indication cohort (ie, on-label cohort): All patients with transfusion-dependent IPSS low- or int-1-risk MDS with isolated del(5q) in the EU who started their treatment after lenalidomide has obtained EU Regulatory approval for the MDS indication and in countries that gave a subsequent positive reimbursement decision.

Other MDS indication cohort (ie, off-label cohort): All patients with any type of MDS other than transfusion-dependent IPSS low- or int-1-risk MDS with isolated del(5q) in the EU who

started their treatment after lenalidomide has obtained EU Regulatory approval for the MDS indication and in countries that gave a subsequent positive reimbursement decision with the exception of eligible patients from the company-sponsored Connect[®] Myeloid Disease Registry (US Cohort Registry) who will be included regardless of start date of treatment.

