7.5 Study Size

The study population will be composed of at least 460 patients with MDS treated with lenalidomide after the granting of Regulatory approval of Revlimid (lenalidomide) for use in the treatment of MDS in the EU (EC Decision, 13-Jun-2013) in the countries concerned. The final data analysis will include all patients eligible for this study at the end of data collection.

An interim descriptive report was prepared 1 year after study start. Within the interim descriptive report, available data on eligible patients regarding the pattern of use of lenalidomide within and outside the EU approved indication, namely the distribution of MDS patients according to predefined categories (eg, transfusion-dependent IPSS low- or int-1-risk MDS with isolated del(5q), or with additional cytogenetic abnormalities, or IPSS risk categories int-2 or high, or patients with MDS without del(5q)) was presented. On 29-Mar-2019, the first interim descriptive report was submitted to the Pharmacovigilance Risk Assessment Committee (PRAC) in order to discuss if the data collected on lenalidomide use, across different groups of MDS patients, are sufficient to allow successful completion of this study. The Assessment Report adopted by the CHMP on 27-Jun-2019 included a request to submit another interim descriptive report in Quarter (Q)1 2020. On 27-Mar-2020, the second interim descriptive report was submitted to PRAC (EMEA/H/C/000717/ANX/041.8). The final Assessment Report, adopted by the CHMP on

10-Dec-2020, concluded that the post-authorisation measure for the second interim report was fulfilled with no further action required.

The data on patients treated with lenalidomide for MDS will only be available within a country following EU-approval of the product for the MDS indication and once available in the selected data source. Therefore, this study will be limited to countries that gave a subsequent decision to fully reimburse lenalidomide for the MDS indication and the extent of data per country will be related to time since the EU-approval for the MDS indication and availability of data with the exception of eligible patients from the company-sponsored Connect[®] Myeloid Disease Registry (US Cohort Registry) who will be included regardless of start date of treatment (see Section 7.4 [Data Sources]).

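### Section 7.1.2.1, read naturally, ties the start of treatment to national reimbursement, while the other eligibility sections tie it to EU approval

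*Protocol*

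**What the plan says.** Section 7.1.2.1 of the protocol opens with "Patients with MDS commencing their treatment with lenalidomide after the granting of Regulatory approval for use in the treatment of MDS in the EU", gives the EC Decision date of 13-Jun-2013, and continues "and a subsequent positive reimbursement decision in the countries concerned, irrespective if the initial MDS diagnosis occurred before (prevalent patients". The criterion then separates incident from prevalent cases by whether the diagnosis came later than 'such date'. Patients in the US Connect registry are exempt from any limit on start date.

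Four other operative places bear on the same question:

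- Section 7.1.1 defines prevalent patients as those diagnosed before EU approval but "whose initiation of lenalidomide treatment occurs on or after the date of EU-approval for the MDS indication". Incident patients are both diagnosed and treated after that date.
- Section 7.1.2.2 excludes "Patients receiving lenalidomide prior to regulatory approval for use in the treatment of MDS in the EU". It does not mention reimbursement.
- Section 7.2.1 defines the overall population as patients "who started their treatment after lenalidomide has obtained EU Regulatory approval for the MDS indication". It adds a condition on where the patient was treated, "and in countries that granted a subsequent positive reimbursement decision with the exception" being the US registry patients.
- Section 7.5 says that "this study will be limited to countries that gave a subsequent decision to fully reimburse lenalidomide for the MDS indication", which is a limit on countries.

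The summary of changes and Section 3 both state that the eligibility date was moved from reimbursement to EU approval in order to gain patients. The summary adds that several patients obtained the drug directly after EU approval without waiting for reimbursement. Its list of sections revised for this change names the Abstract, 6.1, 7.1.1, 7.2.1 and 7.5, but not 7.1.2.1.

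**The concern.** The inclusion criterion decides who enters. Section 7.1.1 itself says that data are collected in line with the inclusion criteria until at least 460 patients are in. If that criterion carries a later start date than the sections around it, the group in dispute is EU patients treated between 13-Jun-2013 and their own country's reimbursement decision. Whether they count would depend on which section a registry follows, and their number would depend on how long each country took to reimburse.

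The off-label proportion is the primary estimate, so its denominator is directly affected. The time-to-AML analyses are also exposed. Section 7.7.3 has each registry run its own Kaplan-Meier and Cox analyses, and Section 7.9 says that pooling raw data is not feasible. A difference in selection inside those analyses would be hard for the sponsor to undo afterwards.

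**Working it through.** **Text comparison.** Take an EU patient who started lenalidomide after 13-Jun-2013, but before a national reimbursement decision that was later granted.

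| Section | Role of EU approval | Role of reimbursement | This patient |
|---|---|---|---|
| 7.1.1 | earliest start date | selects countries | eligible |
| 7.1.2.2 | only earlier starts are excluded | not mentioned | not excluded |
| 7.2.1 | earliest start date | selects countries | eligible |
| 7.5 | earliest start date | selects countries | eligible |
| 7.1.2.1, natural reading | one of two events that must precede the start | the other event that must precede the start | ineligible |

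The difference turns on a few words. Section 7.2.1 inserts 'in countries that' before the reimbursement clause and so makes it a property of the country. Section 7.1.2.1 lacks those words, so the decision becomes a second object of 'after'. The conflict is between current operative sections. The summary of changes is used here only to show intent and to show that the affected patients exist.

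**Prevalent/incident boundary.** Section 7.1.2.1 refers back to 'such date' after naming two events. Sections 7.1.1 and 7.2.1 name EU approval explicitly, using before for prevalent and after for incident. A diagnosis made on 13-Jun-2013 itself falls in neither group.

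**Precision.** The protocol's figure is reproduced first, with the Wald interval p ± 1.96·√(p(1−p)/n):

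- n = 460, p = 0.5: 1.96 × √(0.25/460) = 0.0457, giving 45.4% to 54.6%. This matches Section 7.5.

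The protocol gives no count of patients in the gap. The shares below are assumptions, and they show what would be left if 460 had been reached with these patients included and they were then removed:

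| Assumed gap share | n left | 95% CI at 50% |
|---|---|---|
| 0% | 460 | 45.4–54.6% |
| 5% | 437 | 45.3–54.7% |
| 10% | 414 | 45.2–54.8% |
| 20% | 368 | 44.9–55.1% |

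**Possible shift in the estimate.** If a share g of patients lies in the gap and their off-label proportion differs by d from the rest, including rather than excluding them moves the pooled proportion by g × d. With an assumed g = 10% and d = 20 points, this is 0.10 × 20 = 2 points. Neither input comes from the protocol, so this shows how the shift would scale and is no estimate of its size.

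**The case against.** The strongest reply is that this is loose drafting with a clear intent. The words about a subsequent decision in the countries concerned echo Section 7.2.1 and can, with some strain, be read as a country condition. Every other eligibility section points to EU approval, and Section 3 states the intent outright. The sponsor also undertakes to standardise the criteria for data use (Section 7.9), to keep operational definitions of variables consistent across sources (Section 7.4), and to send statistical framework documents to all data owners for the aggregated analyses (Section 7.7).

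Much of this stands, and it limits what can be claimed. A reader might go further in three ways that the protocol does not support:

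- That registries will select different patients. The alternative reading and the central standardisation make this a possibility only.
- That prevalent and incident patients will be misassigned. The Abstract and Sections 7.1.1 and 7.2.1 define both groups explicitly by EU approval, and the only calendar date in the criterion is 13-Jun-2013. The back-reference is untidy, but misassignment is not shown.
- That the sample falls to 437 or 414, or that the estimate is biased by 2 points. The figure of 460 is a floor to be reached before the final analysis, so a stricter reading would first affect feasibility and timing. The shift rests on two assumed numbers.

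The reply does not remove the conflict. Standardised criteria help only if they rest on one reading, and the section that bears the name of inclusion criteria is the one that departs from the rest.

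**Conclusion.** The point holds as a conflict between operative sections of the protocol. Read naturally, Section 7.1.2.1 bars EU patients who started between 13-Jun-2013 and national reimbursement, and Sections 7.1.1, 7.1.2.2, 7.2.1 and 7.5 let them in. Registries applying 7.1.2.1 literally could use a different denominator for the off-label proportion and would find 460 harder to reach, in a study whose target was already lowered from 500 for want of patients.

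The effect on precision is small: each confidence limit moves by about 0.5 points even if an assumed 20% of 460 are lost. The direction and size of any bias are unknown, because the protocol gives neither the number of patients in the gap nor their off-label share. Only the EU registries are affected, since US Connect patients enter regardless of start date. The case for correction is that a selection rule for the primary estimate should have one meaning.

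**What to change.** Reword the first inclusion criterion so that it matches Section 7.2.1: treatment begun after the EU regulatory approval (EC Decision, 13-Jun-2013), in countries that granted a positive reimbursement decision afterwards. In the same sentence, replace 'such date' with the date of EU approval. Keep the exception for the US Connect registry; a rewrite that dropped it would contradict Sections 7.1.1, 7.2.1 and 7.5. Decide where a diagnosis made on 13-Jun-2013 belongs and say so identically in 7.1.1, 7.1.2.1 and 7.2.1. Carry the same wording into the instructions to the registries before the final extraction.

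The cost is one reworded sentence and a matching word or two in two other sections. An additional estimate of the off-label proportion, restricted to EU patients who started after national reimbursement, would show whether early access was selective. It is optional, is not needed to resolve the conflict, and requires each country's reimbursement date.

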7.1.2.2 Exclusion Criteria

- Patients receiving lenalidomide prior to regulatory approval for use in the treatment of MDS in the EU (EC Decision, 13-Jun-2013) in the countries concerned
- Patients treated with lenalidomide in an interventional therapeutic clinical trial for MDS

7.2 Setting

7.2.1 Study Population and Cohorts

Overall population: Those MDS patients who have received at least one dose of lenalidomide and who started their treatment after lenalidomide has obtained EU Regulatory approval for the MDS indication and in countries that granted a subsequent positive reimbursement decision with the exception of eligible patients from the company-sponsored Connect® Myeloid Disease Registry (US Cohort Registry) who will be included regardless of start date of treatment.

This population will include both prevalent (patients whose initial MDS diagnosis is **prior** to the date of EU-approval for the MDS indication, but whose initiation of lenalidomide treatment occurs on or after the date of EU-approval for the MDS indication) and incident patients (patients whose initial MDS diagnosis and initiation of treatment with lenalidomide is **after** the date of EU-approval for the MDS indication).

MDS licensed indication cohort (ie, on-label cohort): All patients with transfusion-dependent IPSS low- or int-1-risk MDS with isolated del(5q) in the EU who started their treatment after lenalidomide has obtained EU Regulatory approval for the MDS indication and in countries that gave a subsequent positive reimbursement decision.

Other MDS indication cohort (ie, off-label cohort): All patients with any type of MDS other than transfusion-dependent IPSS low- or int-1-risk MDS with isolated del(5q) in the EU who

started their treatment after lenalidomide has obtained EU Regulatory approval for the MDS indication and in countries that gave a subsequent positive reimbursement decision with the exception of eligible patients from the company-sponsored Connect[®] Myeloid Disease Registry (US Cohort Registry) who will be included regardless of start date of treatment.

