7.4 Data Sources

Celgene assessed the feasibility of this protocol using various potential data sources across the EU for the identification of off-label prescriptions and existence of longitudinal data to measure long-term outcomes of patients with MDS, including progression to AML. The sources of data for the primary drug-utilisation objective and the secondary safety objectives in this study will include, but will not be limited to:

- the existing academic EUMDS Registry
- the Spanish Registry of MDS or RE SMD (registro español de síndromes mielodisplásicos), coordinated by the Spanish Group of MDS [GESMD] who aims to promote and develop primary research on MDS, bringing together all those involved in research, diagnosis and management of patients with MDS.
- the Düsseldorf MDS Registry, who aims, as best possible, to biologically characterize MDS, anticipate the course of the disease, and find the most suitable therapies as a benefit for all MDS patients
- the online French Registry of MDS, coordinated by the French MDS group [GFM]), a non-profit organization that includes most French haematology centres, several of them registered as centres of excellence of the International MDS Foundation
- the Danish National Acute Leukemia Registry.

Additionally, the company-sponsored Connect[®] Myeloid Disease Registry (US Cohort Registry) will be used to address the secondary safety objectives (but not the primary drug-utilisation objective due to a different MDS indication approved in the US, which is for the treatment of patients with *transfusion-dependent anemia due to low- or intermediate-1-risk myelodysplastic syndromes [MDS] associated with a deletion 5q abnormality with or without additional*

cytogenetic abnormalities). The company-sponsored Connect[®] Myeloid Disease Registry is a non-interventional, prospective, longitudinal, observational, multicenter, US cohort registry study of patients with confirmed cases of newly diagnosed MDS, idiopathic cytopenia of undetermined significance, and AML.

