7.7.3 Safety Analyses

Safety analyses will be based on both the on- and off-label cohorts.

The cumulative incidence of progression to AML will be calculated and stratified according to predictive factors; 95% CIs will be calculated for each of the two cohorts. Aggregated data will be listed by country when possible.

Each registry will be requested to produce Kaplan-Meier curves for on- and off-label patients separately and to calculate the hazard ratio of on- versus off-label patients. They will also be requested to perform multivariate analyses using a Cox model including and on-/off-label indication and prognostic factors as described in the Statistical Analysis Plan on their own individual data. The respective outcomes will be provided by each registry to the study sponsor. Safety for the on- and off-label cohorts will be determined based on the incidence of reported hematological and non-hematological adverse events including SPM other than AML (which is considered as disease progression in patients with MDS). In particular episodes of neutropenia, thrombocytopenia, venous thromboembolic events, infections, bleeding, major cardiac events and SPM will be collected throughout the observational period of a patient in both cohorts as part of the clinical routine.

Due to the secondary use of the data, individual data may not be available. In these conditions, no explorative analyses on confounding or risk factors is foreseen in the protocol, except for progression to AML.

As there is no international standard to define transfusion dependence and there is a risk of error in transfusion coding, an additional sensitivity analysis will be completed to assess the impact of transfusion on the size of the on- and off-label cohorts. This sensitivity analysis will describe the proportion of off-label patients based only on IPSS categories other than low and int-1, and any karyotype other than isolated del(5q).

All safety analyses will be mainly descriptive or explorative in nature.

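### The US Connect registry is admitted to the off-label cohort but not to the on-label cohort, so some eligible US patients have no proper cohort and the pooled safety summaries compare unlike sources

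*Protocol*

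**What the plan says.** Protocol 7.2.1, repeated in the Abstract under Population and Cohorts, defines three groups. The overall population admits Connect patients as an exception to the EU approval and reimbursement conditions. The on-label definition reads "MDS licensed indication cohort (ie, on-label cohort): All patients with transfusion-dependent IPSS low- or int-1-risk MDS with isolated del(5q) in the EU", adds the approval and reimbursement conditions, and has no Connect exception. The off-label definition covers "All patients with any type of MDS other than transfusion-dependent IPSS low- or int-1-risk MDS with isolated del(5q) in the EU who" began treatment after EU approval. It then adds the condition "in countries that gave a subsequent positive reimbursement decision with the exception of eligible patients from the company-sponsored" Connect registry ("US Cohort Registry) who will be included regardless of start date of treatment").

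Section 7.4 says that Connect "will be used to address the secondary safety objectives (but not the primary drug-utilisation objective due to a different MDS indication approved in the US". Section 6.2.2 sets those safety objectives for both cohorts.

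Section 7.7.3 bases the safety analyses on both cohorts and gives AML cumulative incidence with a 95% CI for each. It then states: "Each registry will be requested to produce Kaplan-Meier curves for on- and off-label patients separately and to calculate the hazard ratio". That ratio compares the two label groups, and a Cox model with a label term follows, fitted by each registry to its own data. Section 7.9 foresees pooling of aggregated data across sources.

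On size, 7.1.1 collects data "according to the inclusion criteria, until at least 460 patients are included". The inclusion criteria in 7.1.2.1 carry the Connect exception.

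**The concern.** The two cohorts should divide the study population by disease profile. As written they also divide it by geography, on one side only. Three things are at stake:

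- US patients whose disease matches the EU label have no clear place. They must be expected, because the US indication quoted in 7.4 covers del(5q) with or without further abnormalities and so includes isolated del(5q).
- One registry is asked for an analysis that it cannot perform.
- In the pooled summaries, an EU-only on-label reference restricted to treatment after 13-Jun-2013 stands beside an off-label group that mixes EU and US patients, with no date restriction on the US part. A difference between these columns could reflect country or period rather than label status.

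**Working it through.** **1. Where a Connect patient falls.** The wording allows three readings of the off-label exception.

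| Reading | US patient with EU-label profile | Other US patient | Connect on-label patients |
|---|---|---|---|
| Admits US patients who meet the off-label disease definition | no cohort | off-label | none |
| Admits every eligible Connect patient | off-label (misclassified) | off-label | none |
| Waives only the start date; the EU restriction still binds | no cohort | no cohort | none |

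The last column is the same throughout. With no on-label patients, Connect can draw no on-label curve, and neither the hazard ratio nor the label coefficient in its Cox model is estimable. All three readings conflict with 6.2.2 and 7.4 taken together.

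**2. The plan's own figures.** Both reproduce, so no stated number is wrong.

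- Off-label proportion (7.5: n = 460, p = 0.50), Wald: 0.50 ± 1.96 × √(0.25/460) = 0.50 ± 0.0457, or 45.4% to 54.6%.
- AML in off-label patients (7.5: n = 230, p = 0.17, so 39 events), Clopper-Pearson: 12.3% to 22.4%.

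**3. How far pooling could shift the off-label AML figure.** Suppose there is no label effect, with a risk of 17% in both EU cohorts (the planning value in 7.5). Let s be the US share of the off-label cohort and r the US AML risk. The protocol gives neither, so both are assumed, with r running from half to twice 17% (8.5% to 34%).

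Pooled off-label risk = (1 − s) × 0.17 + s × r

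| s | r = 8.5% | r = 34% | Ratio to 17% |
|---|---|---|---|
| 10% | 0.153 + 0.0085 = 16.2% | 0.153 + 0.034 = 18.7% | 0.95 to 1.10 |
| 20% | 0.136 + 0.017 = 15.3% | 0.136 + 0.068 = 20.4% | 0.90 to 1.20 |
| 30% | 0.119 + 0.0255 = 14.5% | 0.119 + 0.102 = 22.1% | 0.85 to 1.30 |
| 50% | 0.085 + 0.0425 = 12.8% | 0.085 + 0.17 = 25.5% | 0.75 to 1.50 |

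This applies to the first two readings. Under the third, Connect contributes to neither cohort and there is no shift. Only the last upper value, 25.5%, lies outside the plan's own interval of 12.3% to 22.4%.

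**4. Which analyses are touched.** Kaplan-Meier curves, hazard ratios and Cox models are run inside each registry (7.4, 7.6, 7.7.3). A hazard ratio from an EU registry contains no US patients, so s = 0 and nothing moves. The shift is confined to summaries pooled by cohort: AML cumulative incidence, adverse events and second primary malignancies.

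**The case against.** The best defence is that the asymmetry may be deliberate. The Abstract (Study Size) calls AML progression in off-label patients the main secondary objective, with on-label results for reference, and 5.2 assigns on-label AML progression to a separate registry study, MDS-010. Connect might be there chiefly to enlarge the off-label safety data. Section 7.7.2 also describes the label groups by disease alone, which gives a basis for classifying US patients. In addition, the Abstract rules out a formal safety comparison between label groups, 7.7.3 lists aggregated data by country where possible, and 7.9 promises caution over differences between registries.

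This softens the point without removing it. No text says that Connect is for off-label safety only; 6.2.2 and 7.4 read together say otherwise. Listing by country where possible and cautious wording do not assign the missing patients or give Connect an on-label arm.

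Three stronger inferences are tempting but unsupported:

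- **That country confounds the on/off-label hazard ratios.** They are computed within registries, so EU/US mixing cannot enter them.
- **That US patients inflate the primary off-label proportion.** Sections 7.1.1 and 7.4 exclude Connect from that objective.
- **That the precision of the primary estimate is lost.** The Abstract's Study Size text ties the 460 to reimbursing countries without a Connect exception, its Sample Size Estimation text bases the 460 on the pattern-of-use proportion, and 7.5 opens by tying it to treatment after EU approval in the countries concerned. Against that, 7.1.1 counts by inclusion criteria that admit Connect, and 7.5 later repeats the exception. This is an ambiguity, not a demonstrated loss. If 10% or 20% of the 460 were US patients (assumed), EU n would be 414 or 368 and the Wald interval 45.2% to 54.8% or 44.9% to 55.1%, a small change.

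**Conclusion.** The point stands as an error in the cohort definitions. On any reading Connect has no on-label patients, so 7.7.3 asks it for analyses that it cannot produce, and US patients with the EU-label profile are left out or misclassified. That conclusion needs no assumption about numbers. Where Connect enters the off-label cohort, the pooled safety summaries differ between cohorts in country and permitted calendar period by design.

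The size of any resulting distortion cannot be known from the protocol. Under the assumed ranges it is modest for a small US share (16.2% to 18.7% against 17% at a 10% share) and material only if Connect is large and its risk very different (12.8% to 25.5% at a 50% share). EU within-registry hazard ratios and the stated confidence intervals are not in question. Which patients count toward the 460 needs one clarifying sentence.

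Only the protocol was available. It fixes these definitions itself, so a correction confined to the analysis plan would contradict it.

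**What to change.** - **7.2.1 and Abstract:** for the safety analyses, classify Connect patients by the same EU-label disease criteria as EU patients and write this rule into both cohort definitions.
- **7.7.3:** present Connect as its own stratum beside the EU sources, and report the pooled summaries of AML cumulative incidence, adverse events and second primary malignancies with and without Connect. Connect can then attempt its own on/off-label curves and hazard ratio, as far as its on-label numbers allow.
- **7.5:** add one sentence that the 460 and the off-label proportion with its CI count EU patients only. Restate the CI if fewer EU patients contribute.

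The cost is wording in these sections and one extra stratum in the safety tables. No new data collection is needed for the reclassification.
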